**Data Management**

Data will be collected on standardized case report forms and entered into a HIPAA-compliant electronic database (REDCap) that provides an appropriate interface with a robust statistical

package (Stata ver. 14.2, StataCorp LLC, College Station, TX, USA). All study-related hard copy materials will be stored in locked file cabinets.

### **Data Analysis**

Results of the randomized comparative trial will be determined by an analysis of categorical data from the 3-month follow-up. At 3-month follow-up, prior to allowing crossover, overall treatment response rates (in the previously defined categories of failure or success) will be calculated for both treatment groups using an intention-to-treat analysis. For time periods beyond 3 months, intention-to-treat and as-treated analyses will be performed with primary reporting based on the as-treated analysis to assess the long-term effectiveness of each treatment. In the intention-to-treat analysis, participants who cross-over will be treated as treatment failures of their original group assignment. In addition, a treatment benefit survival analysis will be performed.

Subgroup analyses will be performed to assess treatment response and long-term effectiveness in patients reporting 100% relief from lumbar MBN blocks as compared with those reporting between 80% relief. Data will also be examined to identify any factors that predict treatment success and need for repeat treatment.

Secondary outcomes will be similarly evaluated. For the assessment of function and global quality of life, the proportions of those achieving and not achieving the established minimal clinically important differences (MCID) will be determined and compared between the two treatment groups at the 6-month follow-up. For long-term analysis of treatment effectiveness, an as-treated analysis will determine the proportion of participants exceeding these response thresholds. In addition to these categorical outcomes, changes in group mean scores will be measured and compared.

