As such, the goal of the proposed study is to determine if individuals with lumbar facet syndrome who are treated with C-RFA of the MBNs compared to facet joint injection of corticosteroid have a greater likelihood of experiencing meaningful relief of low back pain symptoms, functional improvement, and reduction of analgesic medication use at both short and long-term follow-up.

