## **Study Timeline**

### *Baseline:*

Participants who meet inclusion and exclusion criteria will be enrolled into the study after consenting to and before receiving treatment. The baseline examination and all baseline questionnaires will be completed within 8 weeks before the index study treatment procedure (facet joint steroid injection or medial branch radiofrequency ablation) as time is needed to obtain insurance authorization for all study procedures in the present study (all procedures in this

study represent usual care procedures: medial branch blocks, facet joint injections, and medial branch radiofrequency ablation).

*Follow-up:*

Routine scheduled follow-up will occur at 1 month (+/- 2 weeks), 3 months (+/- 4 weeks), 6 months (+/- 6 weeks), 12 months (+/- 3 months), and 24 months (+/- 3 months), at which times all follow-up measures will be obtained.

The 3-month follow-up will serve as the time point for the primary outcome analysis of the randomized trial and an intention-to-treat analysis will be used to evaluate for differences in outcomes between the two groups. The 3-month time point provides a reasonable timeframe to evaluate the clinical effects of the lumbar MBN C-RFA while also providing a humane timeframe for crossover to active treatment in those randomized to usual treatment. All subsequent follow-up periods are intended to evaluate long-term clinical outcomes of lumbar MBN C-RFA and will be evaluated with an as-treated analysis.

The study start date and the outcome assessment timeline will begin at the date of the participant's initial facet-targeted treatment. After 3 months, patients who have failed treatment (not meeting criteria for success, as described above) can be offered alternative treatment. Those who cross-over will be considered treatment failures of the original treatment, by definition, and continue on the regular follow-up schedule. A new 2-year follow-up period will begin upon cross-over.

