#### *FJI Procedure (Procedure as performed as standard of care clinical practice)*

During the C-RFA procedure, the participant will be positioned prone on a fluoroscopy table. Sterile precautions, including sterile preparation, drapes, and gloves, will be undertaken.

Using an oblique fluoroscopic view, the image intensifier will be rotated to optimize the posterior joint space opening. A spinal needle will be advanced under fluoroscopic guidance to enter the posterior joint space. The needle position will be confirmed in both AP and oblique views. Approximately 0.2-1 mL of iodinated contrast medium will be injected to confirm intra-articular placement and no vascular uptake. The injection will be then completed with 0.5 mL of 40mg/mL Kenalog and 0.5 mL of 1-4% preservative-free lidocaine. This technique will be repeated for each facet joint injected.

For bilateral low back pain, a maximum of 4 facet joints (two on each side) will be injected. For unilateral low back pain, up to 3 facet joints will be injected.

*Group Assignments:*

Patients will be randomly assigned to the two treatment groups (C-RFA vs. FJI) at a 1:1 ratio. Participants who reported 50% or more relief of their usual pain (NPRS score compared to baseline) at the 3-month follow-up time point and who subsequently experience a treatment effect that diminishes by > 50% will be offered a repeat procedure. Duration of relief will be considered the time from the provision of the treatment procedure until the participant returns to 50% of their pre-treatment level of pain as reported during scheduled follow-up, or when a repeat treatment procedure is requested and performed.

*Crossover:*

Any time after the 3-month follow-up, any participant who has not obtained adequate pain relief can ask to cross over to alternative treatment group. In doing so, a new 2-year follow-up will begin for this participant who is now placed in the alternative treatment group for the long-term, as-treated outcomes analysis.

*Co-interventions:*

Patients are allowed to receive usual care, including co-interventions, as deemed necessary by the treating physician. Treatments related to the participant's spine condition will be reported on the ancillary treatment log.

*Primary Outcomes:*

The primary outcome for the randomized trial is the proportion of responders, defined by a reduction in NPRS score  $\geq 50\%$  at the 3-month follow-up.

*Secondary Outcomes:*

1. Physical function (ODI and PF CAT)

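### No analysis names the 1-month visit, and the planned two-sample tests of the continuous outcomes use neither baseline as a covariate nor the 1-month score; a baseline-adjusted mixed model over 1 and 3 months would be more precise.

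*Combined protocol and SAP*

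**What the plan says.** The Follow-up part of the Study Timeline sets the visits: "Routine scheduled follow-up will occur at 1 month (+/- 2 weeks), 3 months (+/- 4 weeks), 6 months (+/- 6 weeks", then 12 and 24 months, "at which times all follow-up measures will be obtained". The full outcome set is therefore available at 1 month.

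The same section fixes the primary time point: "The 3-month follow-up will serve as the time point for the primary outcome analysis of the randomized trial". The Crossover paragraph then states: "Any time after the 3-month follow-up, any participant who has not obtained adequate pain relief can ask to cross over to alternative treatment group". So 1 and 3 months are the only scheduled visits before crossover opens.

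Data Analysis opens with the statement "Results of the randomized comparative trial will be determined by an analysis of categorical data from the 3-month follow-up". The comparisons there that carry a time are these:
- responder rates by intention to treat: "At 3-month follow-up, prior to allowing crossover, overall treatment response rates";
- later periods, by intention to treat and as treated, with the as-treated result reported first;
- proportions reaching the MCID for function and global quality of life, at 6 months.

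Three statements there carry no time: that secondary outcomes are handled in a similar way, that changes in mean scores are compared, and that a survival analysis of treatment benefit is done. Statistical Analysis compares quantitative variables by two-sample t-test or Wilcoxon-Mann-Whitney test. It mentions no covariate and no model across visits.

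**The concern.** Two things are at stake, both in the secondary outcomes.

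The first is specification. The 1-month visit is one of only two at which the groups are compared free of crossover, and the plan does not say whether or how they are compared there. Because the mean-score comparison has no stated visit, the choice of visit could be made after the data are seen.

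The second is efficiency. NPRS, ODI, PF CAT, Global-10 and the MQS III score are all recorded at baseline, 1 month and 3 months. A two-sample test at a single visit makes poor use of this. Subtracting baseline is less precise than adjusting for it, and a participant who misses the 3-month visit drops out of the comparison even if the 1-month score is known. The Power Analysis expects attrition, so some 3-month scores will probably be missing.

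**Working it through.** **The plan's own figure.** Power Analysis: 80% vs 50% responders, two-sided alpha 0.05, power 0.80, chi-square. With the mean proportion 0.65,

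n = [1.960·√(2·0.65·0.35) + 0.842·√(0.8·0.2 + 0.5·0.5)]² / 0.30² = (1.322 + 0.539)² / 0.09 = 38.5, so 39 per group.

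This matches the plan. With all 135 enrolled (68 and 67), Fisher's exact test has 96% power for the same rates. Nothing below changes the primary analysis.

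**Inputs for the precision check.** The documents give no correlations and no attrition rate, so the following are assumptions:
- ρ, correlation of baseline with each follow-up score: 0.3 to 0.5;
- r, correlation of the 1- and 3-month scores: 0.5 to 0.7;
- m, fraction of 3-month scores missing: 0.2;
- equal variances at all visits.

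**Step 1: baseline as a covariate.** In units of the score variance, a change score has variance 2(1 − ρ), and a baseline-adjusted score has 1 − ρ². The ratio is (1 + ρ)/2, so the reduction is (1 − ρ)/2.
- ρ = 0.3: (1 − 0.3)/2 = 35%.
- ρ = 0.5: (1 − 0.5)/2 = 25%.

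If the t-test were instead run on the 3-month score itself, the reduction would be ρ²: 9% at ρ = 0.3 and 25% at ρ = 0.5.

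**Step 2: adding the 1-month score.** Once baseline is in the model, the relevant quantity is the partial correlation

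r_p = (r − ρ²)/(1 − ρ²).

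With a fraction m missing at 3 months and every 1-month score observed, the variance of the 3-month mean is proportional to 1/(1 − m) for complete cases and to (1 − r_p²)/(1 − m) + r_p² for the joint model. The relative reduction is r_p²·m.

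| r | ρ | r_p | Reduction at m = 0.2 |
|---|---|---|---|
| 0.5 | 0.5 | 0.25/0.75 = 0.333 | 0.111 × 0.2 = 2.2% |
| 0.7 | 0.3 | 0.61/0.91 = 0.670 | 0.449 × 0.2 = 9.0% |

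Ignoring baseline, r²·m would give 5.0% to 9.8% for r = 0.5 to 0.7. The lower end falls to 2.2% once baseline is in the model.

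**Step 3: sensitivity.** If half of those missing at 3 months also lack a 1-month score, the observed fraction at 1 month is 0.9, and the reduction becomes r_p²·(0.1/0.9): 1.2% to 5.0%. If nobody is missing at 3 months, it is zero. Most of the gain therefore comes from baseline adjustment.

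**The case against.** A reader might infer that the 1-month data are shut out of the analysis and that half of the intact randomised follow-up is wasted. The documents do not support that. The three undated statements could take in 1-month data. Duration of relief, as defined under Group Assignments, runs from the procedure and is read at scheduled visits, of which 1 month is one. What stands is silence, not exclusion. One half is also true only by visit count; by elapsed time, 1 month is a third of the pre-crossover period.

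A reader might also infer that an early advantage of the steroid injection is being hidden, and ask for a formal 1-month responder test. No stated aim requires one. Specific Aim 1 asks for response at 3 months and for duration of relief, and the Background goal of a comparison "at both short and long-term follow-up" names no visit. No figure in the documents points to an early steroid advantage; the success rates given for the injection (42% and 50%) are at 3 months. Such a test would also be weak. For assumed rates of 60% vs 40%, Fisher's exact test has 61% power with 68 and 67 participants and 45% with 54 per arm; for 50% vs 40% it has 18% with 68 and 67.

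Two further objections stand in part. A single primary time point is legitimate, and the plan gives reasons for choosing 3 months. A mixed model also gives up the rank-test option for skewed data unless this is dealt with explicitly.

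**Conclusion.** The point holds as a low-cost improvement to the secondary analyses. No analysis names the 1-month visit, and the planned tests of quantitative outcomes neither adjust for baseline nor use the 1-month score where the 3-month score is missing. The 3-month responder comparison and its sample size stand.

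Against a change-score t-test, baseline adjustment reduces variance by about 25% (ρ = 0.5) to 35% (ρ = 0.3), which is a standard error about 13% to 19% smaller (1 − √0.75 and 1 − √0.65). The 1-month score then removes about 2% to 9% of the remaining variance, given 20% missing at 3 months and 1-month scores for those participants. All these sizes rest on the assumed correlations and missing fraction. The documents do not support saying that the trial's main conclusion is at risk.

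**What to change.** In Data Analysis and Statistical Analysis, specify the following:
- NPRS, ODI, PF CAT and Global-10 at 1 and 3 months are each analysed by randomised group in one mixed model with arm, visit, arm-by-visit interaction and baseline score. This replaces the separate t-tests or Wilcoxon-Mann-Whitney tests at these visits.
- The 3-month contrast is the main secondary result for each score. The 1-month contrast is reported beside it as supportive.
- The MQS III score is treated the same way, with the rank test kept as a sensitivity analysis if its distribution is skewed.
- The plan states whether 1-month pain scores feed the survival analysis.

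The cost is a few lines of text and a standard model in the planned software, with no new data and no change to the primary analysis or sample size. There are three downsides. The change adds one 1-month contrast for each of the five scores, which should be labelled not confirmatory because the plan uses 0.05 for every test. The model assumes approximate normality. It also assumes that a missing 3-month score depends only on arm, baseline and the 1-month score.

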### *Statistical Analysis*

Descriptive statistics and graphical displays will be used to examine the central tendency and distribution of each outcome variable. Data will be analyzed using Stata (ver. 14.2, StataCorp LLC, College Station, TX, USA). An alpha level of 0.05 and two-tailed tests will be used for all hypothesis testing.

To illustrate the demographic, radiologic, and procedural characteristics of the study sample, means and standard deviations or medians and interquartile ranges (depending on the distribution of data) will be calculated for continuous variables, and frequencies and proportions will be calculated for categorical variables. Demographic, clinical, and radiologic differences will be compared between the groups (C-RFA vs. FJI) in order to ensure that the two groups are equal in terms of observed as well as unobserved covariates other than the treatment provided to them.

In comparing groups (C-RFA vs. FJI) with regard to categorical variables, Fisher's exact tests will be used. Proportions and 95% confidence intervals will also be calculated in order to confirm that any differences between groups are truly distinguished. A proportion ratio will be calculated as the measure of the effect size. For quantitative variables, independent *t*-tests or Wilcoxon-Mann-Whitney tests will be used to compare means or medians, respectively. An effect size of *r* will be calculated to examine the magnitude of a group difference.

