### **1.0 Research Aims:**

#### **1.1 Research Question:**

Does Cooled Radiofrequency Ablation (C-RFA) of the medial branch nerves (MBN) compared to zygapophyseal (“facet”) joint injection of corticosteroid result in a greater response rate defined by meaningful relief of low back pain symptoms, functional improvement, and reduction of analgesic medication use in individuals with lumbar facet syndrome?

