**Power Analysis**

In the Dreyfuss et al prospective cohort study of conventional RFA for the treatment of chronic lumbar facet joint pain, which used an identical diagnostic/selective MBN block protocol (SIS guidelines), to that of the proposed study, 87% of patients experienced at least 60% reduction in pain at 10-month follow-up. For the present power analysis, we will more conservatively estimate a success rate of 80%, using 50% relief in pain at 3 months as the definition of success.

No study to date has used dual comparative MBN blocks to select patients for facet joint injection of corticosteroid. However, Carette et al. used intra-articular injection of local anesthetic only (>50% relief considered “positive) in order to select patients for a randomized controlled trial of lumbar facet joint injection of corticosteroid versus saline. In this study, a 42% success rate was observed at 3 months. For the present power analysis, we will more conservatively estimate a success rate of 50% at 3 months, as participants will be selected by dual comparative MBN blocks rather than only one intra-articular diagnostic injection.

Given that the primary analysis will be categorical in nature (comparison of the proportion of responders), with an alpha level of 0.05 and a power of 0.80, 39 participants would be needed in each group (total 78 participants) to detect a significant difference in the proportions between the two groups (80% vs. 50%) using a chi-square test. However, in order to improve the power of the study beyond the minimally acceptable standard and to account for anticipated attrition, we propose to enroll 135 patients in the trial.

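### The plan tests every secondary comparison at two-sided 0.05 with no order, adjustment or exploratory label, although the research question covers function and analgesic use

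*Combined protocol and SAP*

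**What the plan says.** The Statistical Analysis section sets one rule: "An alpha level of 0.05 and two-tailed tests will be used for all hypothesis testing". No section gives a testing order, a multiplicity adjustment or a key secondary family, or marks any analysis as exploratory.

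The primary outcome is one endpoint at one visit: the proportion with at least a 50% NPRS reduction at 3 months. The secondary efficacy outcomes are ODI, PF CAT, Global-10, MQS III and PGIC. The Specific Aims add daily morphine equivalents. The Study Timeline has all follow-up measures taken at 1, 3, 6, 12 and 24 months.

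The Data Analysis section compares function and global quality of life as MCID proportions, naming the 6-month visit for the between-group comparison. It then adds a second form: "In addition to these categorical outcomes, changes in group mean scores will be measured and compared". Beyond 3 months it calls for both intention-to-treat and as-treated analyses, with the as-treated results reported as primary. It also includes a subgroup analysis by degree of block relief and an open search: "Data will also be examined to identify any factors that predict treatment success and need for repeat treatment".

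The Research Question frames the claim as "meaningful relief of low back pain symptoms, functional improvement, and reduction of analgesic medication use", and the Null Hypothesis repeats all three parts.

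**The concern.** The primary test covers only the pain part of the research question. The other two parts, function and analgesic use, rest on secondary tests, and the plan does not say which of those tests counts. Each instrument can be tested at several visits, some in two forms, and after 3 months in two analysis sets. A reader of the results could not tell a significant ODI difference that was planned as the key test from one chosen among many. A chance finding on function or analgesic use could then be reported as confirming part of the stated hypothesis. The predictor search has the same weakness: no factor list, no model and no label.

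**Working it through.** **The plan's own figure.** The Power Analysis gives 39 per group for 80% vs 50%, alpha 0.05, power 0.80, chi-square. With pooled variance, mean proportion 0.65 and a two-sided test:

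n = [1.960 × √(2 × 0.65 × 0.35) + 0.842 × √(0.80 × 0.20 + 0.50 × 0.50)]² / 0.30² = (1.322 + 0.539)² / 0.09 = 38.5, so 39 per group.

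This reproduces the plan. It uses the full 0.05 on one test, so the primary comparison carries no multiplicity. The plan gives no familywise error rate and no count of secondary tests, so everything below is conditional on stated assumptions.

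**Independent tests.** The chance of at least one false positive among k tests is 1 − 0.95^k in either direction and 1 − 0.975^k favouring C-RFA.
- k = 5: 1 − 0.95⁵ = 0.226; favouring C-RFA 1 − 0.975⁵ = 0.119.
- k = 13: 0.487. k = 14: 0.512, the first value above one half.
- Favouring C-RFA, one half is first passed at k = 28 (0.508).

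**Correlated tests.** The instruments measure related things, so independence overstates the risk. The documents give no correlations. The assumptions are 0.3 to 0.7 between instruments, 0.6 between visits, and 0.75 between an MCID test and the mean test of the same instrument. Correlated normal test statistics were simulated with no true difference, and a result was counted as significant when |z| > 1.96.

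| Tests performed | Either direction (r = 0.7 to 0.3) | Favouring C-RFA |
|---|---|---|
| 5 outcomes, one visit, one form | 15-21% | 7-10% |
| 32 tests: (5 scores + 3 MCID proportions) × 4 visits, one analysis set | 49-62% | 25-34% |
| The same 32, MCID tests at Fisher's true size of about 0.03 | 44-57% | not tabulated |
| 20 of the 32: ODI, PF CAT, MQS III and two MCID proportions × 4 visits | 39-47% | 20-25% |

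The third row is there because the plan uses Fisher's exact test for categorical variables. At 39 to 67 per arm its actual size is about 0.027-0.034, not 0.05. The second and third rows together give the 44-62% range. The expected number of false positives among 32 tests at nominal size is 32 × 0.05 = 1.6.

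**Effect of the remedy.** Holm on five outcomes starts at 0.05 / 5 = 0.01 and keeps the chance of any false claim in that family at or below 0.05, whatever the correlations. Testing the family only after a significant primary leaves the primary at 0.05 and the 39 per group unchanged.

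**The case against.** The best defence is that the trial has one primary test and that the Data Analysis section says the randomised comparison is determined by it. Secondary results in such a trial are often read as supportive. The plan already requires 95% confidence intervals for proportions and effect sizes, and it names as-treated as the primary reporting set after 3 months. The number of tests is nowhere stated: the only visit named for the between-group MCID comparison is 6 months, so repeating it at four visits is an assumption. These points stand, and they limit the size of the problem. They do not remove it, because the research question and null hypothesis include function and analgesic use, and no text marks those tests as supportive.

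A reader might go further and infer that a false claim of functional or analgesic benefit is more likely than not. The documents do not support that. In the 32-test case, the figures above one half count false differences in either direction across all five instruments, and they drop below one half over part of the assumed range. For benefit of C-RFA the figure is 25-34%, and 20-25% on the function and analgesic measures alone. Larger assumed counts that use both analysis sets and both forms (60-68 tests) give 34-63% favouring C-RFA, so one half is passed over only part of that range.

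A reader might also count the subgroup analysis and predictor search towards false functional claims. Both concern treatment response, its duration or repeat treatment, with success defined on pain. They can yield false predictors or subgroup findings, but they add little or nothing to false claims on function. The plan gives no number of candidate factors, so no error rate can be attached to the search.

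**Conclusion.** The point holds as a gap in the plan: 0.05 applies to every test, and nothing separates a confirmatory secondary result from one picked among many. At the least, with each of five outcomes tested once at one visit, the chance of some false significant difference is 15-21%, three to four times the nominal 5%. With 32 tests it is 44-62% in either direction and 25-34% favouring C-RFA. These figures rest on assumed correlations and, for the larger one, an assumed count. They also take the as-treated tests to have their nominal size; those comparisons are no longer randomised after crossover, which is a separate matter. The primary conclusion is not affected. This is a cheap improvement, not a flaw that threatens the trial.

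**What to change.** Amend the Statistical Analysis and Data Analysis sections as follows.

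1. Two-sided 0.05 applies to the 3-month responder comparison.
2. If that is significant, ODI, PF CAT, Global-10, MQS III and PGIC are each compared once by intention to treat, in one pre-named form and at one pre-named visit, with Holm adjustment at overall 0.05. Three months is the randomised comparison before crossover, but the Data Analysis section places the MCID comparison at 6 months. The sponsor must reconcile the two and state one visit.
3. The other visits, the as-treated results, the second form of each outcome and the subgroup results are reported as estimates with 95% confidence intervals and labelled exploratory. The long-term results stay in the report as descriptive evidence, since long-term follow-up is a stated goal.
4. The predictor search is labelled hypothesis-generating, with a short factor list fixed before analysis and treatment arm in the model.

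The cost is wording plus some lost claims. Secondary results with p between about 0.01 and 0.05, and isolated p-values at later visits, could no longer be called significant. No extra participants are needed.

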#### **1.3 Specific Aims:**

1. Determine the proportion of patients with a successful response (defined as 50% or greater improvement in index pain) to lumbar MBN C-RFA versus facet joint injection of corticosteroid at 3 months, and the duration of relief up to 2 years.
2. Evaluate the functional improvement observed in both groups, as assessed by the Oswestry Disability Index (ODI), the PROMIS Physical Function CAT (PF-CAT), and the Patient Global Impression of Change (PGIC); determine the correlation between reduction in pain and improvement in function, as well as the correlation between the

ODI and the PF-CAT in this specific population, to both the anchor score (PGIC) as well as to each other (ODI vs. PF-CAT).

4. Evaluate changes in opioid and non-opioid analgesic use in both groups, as assessed by the conversions to daily morphine equivalent use and Medication Quantification Scale III score.
5. Evaluate differences in the proportion of patients with a successful treatment response in those who reported 100% relief from dual comparative diagnostic lumbar MBN blocks relative to those with at least 80% improvement but less than 100% relief from the dual comparative blocks.
5. Report immediate, short-term, and long-term adverse effects, using a standardized survey that includes a comprehensive query of known adverse events associated with systemic steroid effects.

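### Baseline comparisons are given a purpose they cannot serve, and baseline pain and block relief are not used as covariates in an otherwise valid primary comparison

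*Combined protocol and SAP*

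**What the plan says.** The Statistical Analysis section states: "Demographic, clinical, and radiologic differences will be compared between the groups (C-RFA vs. FJI"), and gives the purpose as "in order to ensure that the two groups are equal in terms of observed as well as unobserved covariates". The paragraph after it assigns Fisher's exact test to categorical variables, and t-tests or Wilcoxon-Mann-Whitney tests to quantitative ones, for comparisons of the two arms. The same section adds: "An alpha level of 0.05 and two-tailed tests will be used for all hypothesis testing". Significance testing of baseline variables is therefore the natural reading, although the baseline sentence does not itself mention p-values. No action is attached to the result.

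For the primary outcome, Data Analysis says that "overall treatment response rates (in the previously defined categories of failure or success) will be calculated for both treatment groups" by intention to treat. No covariate, model or stratification factor is named anywhere. Two baseline quantities have a limited role:

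- **Baseline NPRS** is the reference value for the 50% reduction that defines a responder (Group Assignments; Primary Outcomes).
- **Block relief** is a subgroup factor. Section 1.3 compares "those who reported 100% relief from dual comparative diagnostic lumbar MBN blocks" with those who had at least 80% but less than 100%, and Data Analysis repeats this as a subgroup analysis.

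Data Analysis also plans an open search for predictors of success and of repeat treatment.

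**The concern.** Randomisation balances measured and unmeasured factors in expectation. A later comparison of measured ones cannot improve on that or verify it. If allocation was sound, every significant baseline difference is by definition a chance finding. A non-significant result may only reflect limited power to see an imbalance.

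Two things are at stake. First, a report that follows the plan literally would present balance on unobserved factors as something the analysis had established. Second, the plan tests for imbalance but does not say what follows, and it also leaves the search for predictors open. The choice of adjustment covariates is thus not fixed before the data are seen. Meanwhile two values known before treatment, and plausibly related to response, are left out of the primary comparison, which may give up precision at no saving.

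**Working it through.** **1. The plan's own figure.** Power Analysis says "with an alpha level of 0.05 and a power of 0.80, 39 participants would be needed in each group", for 80% versus 50% with a chi-square test. With pooled proportion 0.65:

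n = [1.960 × √(2 × 0.65 × 0.35) + 0.842 × √(0.80 × 0.20 + 0.50 × 0.50)]² / 0.30² = 38.5, rounded up to 39.

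The figure reproduces. It uses no covariates, and adjustment would not alter it.

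**2. False alarms in baseline testing.** Outcome Instruments lists about 13 baseline items: age, sex, BMI, pain duration, nature of pain, location, block relief, two NPRS versions, ODI, PF-CAT, Global-10 and analgesic use. Radiologic variables are extra. For k independent tests, each at exactly 5%, the chance of at least one significant result is 1 − 0.95^k:

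| k | Chance of at least one |
|---|---|
| 10 | 40% |
| 13 | 49% |
| 15 | 54% |

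The scores are likely to be correlated. With an assumed common correlation of 0.3 to 0.5, the chance falls to about 35% to 29% for 10 variables and 46% to 36% for 15. Fisher's test, being conservative, would lower it further.

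**3. What a non-significant test shows.** The plan states "we propose to enroll 135 patients in the trial", or about 67 per arm. The standard error of a standardised difference is √(2/67) = 0.173.

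- A chance imbalance above 0.2 SD in any one covariate has probability 2 × [1 − Φ(0.2/0.173)] = 25%.
- A true 0.25 SD imbalance is flagged with probability of about Φ(0.25/0.173 − 1.96) = 30%.
- A true 0.30 SD imbalance is flagged about 41% of the time.

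**4. What adjustment could add.** The documents give no prognostic strength for any baseline variable and no attrition rate, so these inputs are assumed: 57 analysed per arm (114 of 135, or 84%); odds ratio 2 for block relief, with half the patients at 100% relief; and a second covariate with odds ratio 1.3 to 2.2 per SD. Unadjusted power is computed exactly, and does not depend on covariate strength once the arm rates are fixed. Adjusted power is from simulation (4,000 trials per setting, Monte Carlo error about 1 point), using the likelihood-ratio test for arm in a logistic model. The ranges cover repeated runs.

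| Response rates | Fisher | Chi-square | Adjusted | Gain over chi-square |
|---|---|---|---|---|
| 80% vs 50% (planned) | 90% | 93% | 94–96% | about 1–3 points |
| 75% vs 50% | 73% | 80% | 81–87% | about 1–6 points |

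The gain is taken against chi-square within the same simulated trials. With no treatment effect the adjusted test rejected about 5% to 6% of the time, so the smallest gains are within noise. The further gap down to Fisher's test is that test's conservatism and is not a benefit of adjustment.

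**The case against.** The strongest reply is that nothing inferential is wrong. Allocation is randomised 1:1, the primary comparison of responder proportions is specified in advance by intention to treat, and no result depends on the baseline comparison. The faulty wording is one clause in a descriptive paragraph, and covariate adjustment is an option, not a repair. All of this stands, and it limits the point to rationale and precision.

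Several stronger readings are tempting but not supported:

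- **That the primary result would be biased or the sample size wrong.** The unadjusted test is valid under randomisation, and the 39 per group reproduces.
- **That the primary is short of power without adjustment.** At the planned rates and 57 per arm, even Fisher's test has about 90%.
- **That the plan expects block relief to predict success.** It proposes to evaluate the difference and states no expectation.
- **That the baseline data are ignored.** Baseline NPRS is built into every responder call, and block relief has its own subgroup analysis. What is missing is their use as covariates.
- **That the investigators will adjust ad hoc.** The plan does not say so. It only fails to rule it out.

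It is also fair to say that the gain may be small. Entry requires an NPRS of at least 5 and at least 80% relief on both blocks, so both covariates have a restricted range.

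**Conclusion.** The point holds as a false rationale plus an avoidable loss of precision. That the stated purpose is unattainable follows from the wording alone and needs no assumption. The 40% to 54% chance of a spurious significant difference assumes 10 to 15 independent tests, and is lower with correlated variables. The gain from adjustment rests wholly on assumed prognostic strengths, and could be near zero if the covariates are weak. The change is worth making because it costs almost nothing and settles the covariate choice before the data are seen, not because the primary conclusion is in danger.

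**What to change.** 1. In Statistical Analysis, delete the clause about ensuring equality on observed and unobserved covariates, and drop significance tests of baseline variables. Present baseline data by arm descriptively, with standardised differences.
2. Pre-specify one covariate-adjusted analysis of 3-month response: a logistic model with arm, baseline 7-day NPRS and block relief. Standardise it marginally to the plan's own effect measure, the proportion ratio, with a 95% CI. A risk difference may be added.
3. Define the block-relief category as 100% on both blocks versus any other qualifying response. Section 1.3 does not place a patient with 100% on one block and less on the other, and Data Analysis leaves the bounds of the lower category incomplete.
4. Report the adjusted and unadjusted comparisons together, state in advance which is primary, and state that covariates will not be chosen from observed imbalances. Confirm that both covariates are recorded before allocation is known.

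The cost is one extra model and a few sentences. Eligibility already requires a baseline NPRS and both block results, so no patients, visits or data items are added. The downside is a small return if the covariates prove weakly prognostic.
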